Eligibility. Subjects eligible for inclusion in the study must be: pregnant women who are admitted to a Labor and Delivery unit for management or induction of labor in the first stage of labor, are able to give informed consent, are 18 years of age or greater, English-speaking, have intact membranes, and have a gestational age greater than or equal to 37 weeks (i.e. term pregnancy). Inclusion criteria also include having a functioning epidural in place or having provided consent prior to the start of labor. Exclusion criteria include progression to the second stage of labor (i.e. known dilation of ten centimeters), non-English speaking, known prior rupture of membranes, any condition that renders labor unsafe for the patient (e.g. cardiac conditions, pulmonary hypertension) and any other condition that necessitates an emergent or urgent cesarean section (e.g. non-reassuring fetal status, placental abruption, hemorrhage, cord prolapse). Patients are only consented if they have adequate pain control, either because they are not yet in labor (i.e. are admitted for an induction of labor) or have a functioning epidural. All participants are necessarily female due to the subject matter. Given the vulnerability of pregnant patients under the age of 18, this study will exclude children. There are no restrictions on eligibility based on race or ethnicity. Patients can withdraw from participation at any point in the study. DilaCheck® is FDA-cleared for use by qualified healthcare professionals for women in pregnancy and labor without any further restrictions.

Provider Enrollment. The Sponsor, TJU Principle Investigator, or trial coordinator will discuss participation in the trial with providers at the TJU Labor and Delivery unit. Providers will be given the option of participating on a volunteer basis.

Provider Training. The Sponsor will train participating providers in the use of the device. The Sponsor will use a detailed script to ensure standardization of the training. The Sponsor will use a wooden cervical simulator box to train providers to use the study device without patient involvement. The standardized training will test competency with the device using the cervical simulator. The providers will also have access to a training video to reinforce the in-person training.

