Trial Coordination. After training, the Sponsor or the trial coordinator will orient the provider to the study protocol and assign every provider a unique Provider Number. The trial coordinator will arrange with the hospital staff to conduct the trial at scheduled times during the study period. Administration of the trial requires two hospital providers who have been trained to use the device, the trial coordinator,

and a patient.

Patient Enrollment. Hospital providers will screen patients who have been admitted to the Labor and Delivery unit for eligibility. Posters advertising the trial will also be displayed on the Labor and Delivery unit. Once identified, hospital providers will ask eligible patients if they are interested in participating. If a patient indicates interest, the trial coordinator will complete an informed consent. The patient will sign the Patient Informed Consent Form.

Randomization. The trial coordinator will assign the participant a Subject Number from one to 50, in sequential order. (The first patient enrolled is assigned #1, the second enrolled is assigned #2, and so on.) The trial coordinator will then randomize the patient to either the Control Group or the Device Group using a randomization matrix generated by a computer randomization program.

Data Collection. The trial coordinator will inform two trained providers that the patient has agreed to participate in the trial. The trial coordinator will accompany one hospital provider to the patient's hospital room. The second provider will wait outside the room, in a place where s/he cannot hear the interaction in the room. The trial coordinator will re-affirm consent with the patient.

If the patient is randomized to the Control Group: The first provider will introduce him/herself and inform the patient that s/he is going to conduct a cervical examination. The trial coordinator will record the time of the first exam. The provider will complete a cervical examination following the standard techniques s/he uses on a regular basis, using sterile gloves. The provider will dispose of the gloves. The first provider will write his/her measurement of cervical dilation on the first Data Collection Form and fold the sheet of paper. Readings may be integers or fractional answers. The coordinator will take the folded sheet of paper and will not read the value. The first provider will then leave the hospital room. S/he will not speak to the second provider.

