Photograph Review. The Sponsor will train an independent reviewer to read DilaCheck® measurements. The reviewer will be provided the photographs taken of DilaCheck® measurements. The reviewer will report two measurements for each photograph. The first will be his/her reading of the exact DilaCheck® measurement, which may be a fraction. The second reading will be his/her reading of the DilaCheck® measurement rounded to the nearest integer; i.e. the second response can only be an integer, not a fraction.

Continuous Feedback. After any individual provider completes five examinations with DilaCheck®, the provider will be provided feedback about whether his/her DilaCheck® measurement readings match those of the independent reviewer.

Power Calculation. The planned enrollment in the study is 50 patients. The following assumptions were used for the power calculations. The agreement in the Control Group was projected to be 49%,⁴ and the agreement in the Device Group was projected to be 90%, based on the results of the simulator trial. The standard deviation was projected to be 23, also based on the standard deviation in the prior simulator trial. With a two-tailed test with $\alpha=0.05$, a sample size of five yields 80% power. However, a trial with five participants will not yield the desired robustness in evaluation of a novel medical device. Instead, a sample size of 25 subjects in each group is planned to allow for examinations across a wide range of patients and providers. A sample size of 50 yields a power of 100% to detect a difference between the two methods given the above assumptions.

Statistical Analysis. The statistical analysis will use a two-tailed level of significance of 0.05. Using SPSS, the proportion of examinations in each group for which the two providers' examinations differed will be determined. A Students T test will be performed to determine whether this difference is significant. The number of examinations for which providers' answers differed by one centimeter and by two or more centimeters for each group will be determined. A Students T test will be performed to determine if the frequency of variation of one centimeter significantly differed between groups. A Students T test will be performed to determine if the frequency of variation of two or more centimeters significantly differed between groups. These analyses will be completed for both the fractional and integral (non-fractional) sets of DilaCheck® measurement readings.

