With regard to missing data, if a patient is missing one or both of the cervical dilation readings, she will be excluded from analysis of the primary outcome. However, if she has filled out a survey, this data will be used in the analysis of secondary outcomes since it may include important data accounting for why the patient was unable to have both examinations. If a patient or provider is missing one or more answers to a survey question, then the response to that question will be omitted from the analysis. The statistical analysis will not include imputing missing data.

The Sponsor will provide the trial coordinator, principle investigator, and other

involved TJU staff access to the statistical analysis and article draft and provide them with time to provide feedback and insight into all statistical analyses.

Study Device Specifications. There are no hazardous materials involved in this trial. The study device is made of soft, medical grade, biocompatible components. The device is sterilized using gamma radiation. The device is not anticipated to present any risk above that of a standard cervical dilation examination with a sterile glove. It is tested for reliability, and all components have multiple attachment points so that if one attachment point fails, it will still be attached to another component or the provider's hand and thus will not be left in the patient.

Bias. Unfortunately, it is not feasible to blind patients and providers to group assignment. However, keeping the second provider blinded to the first provider's measurement will decrease bias. Randomization using a computer generation program will also eliminate assignment bias.

Potential Problems. Given the acuity of Labor and Delivery, one anticipated challenge is enrollment. Women in labor may be hesitant to participate in any clinical trial or to participate in the validation of a novel device. We will offer a small incentive for participation via a modest gift certificate of a size not large enough to coerce patients into participating. The trial coordinator will answer any questions the patient has regarding the trial and respond to any concerns that arise in an open, patient, and honest manner.

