Potential Risks of Study Participation. The device is not anticipated to present any risk above that of a standard cervical dilation examination with a sterile glove. Potential risks to the patient include loss of confidentiality, discomfort with cervical examinations, a theoretical increased risk of infection, rupture of membranes, and inconvenience. For the provider, there is not anticipated to be any risk above that of performing a standard cervical dilation examination with a sterile glove.

Recruitment and Informed Consent. The sampling plan will ensure that all eligible patients are offered the opportunity to participate, regardless of race, ethnicity, or

socioeconomic status. The trial coordinator will consent patients in a private room or area. Consent will be documented with signatures of the trial coordinator and the patient on the Patient Informed Consent Form. Patients will receive a copy of the Patient Consent Form.

Randomization. Patients will be randomized to a treatment group using a computer-generated randomization program to eliminate assignment bias.

Confidentiality. Only the trial coordinator, the Sponsor, and the PI will have access to individually identifiable private information about human subjects. The hospital providers will likely have access to this information through the hospital medical record, but they will not be provided with the data through participation in the trial. The trial coordinator will store trial materials in a locked space at TJU. All physical materials obtained by Elm Tree Medical will be stored in a locked file at the Elm Tree Medical Inc. office. The trial coordinator will provide Elm Tree Medical with an electronic report of data collected. Any data entered into electronic form on TJU or Elm Tree Medical computers will be password-protected.

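### Examiners are masked to each other's study reading but not to an earlier clinical dilation; if both know the same value, control agreement may rise and the contrast between arms may shrink

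*Combined protocol and SAP*

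**What the plan says.** **Masking.** Under Data Collection, the second provider waits out of earshot, forms are folded, and the first provider does not speak to the second. The Bias paragraph concedes that group assignment cannot be masked and names one safeguard for the readings: "keeping the second provider blinded to the first provider's measurement will decrease bias". Nothing is said about a dilation measured before the study examinations.

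**Who screens and who examines.** Under Patient Enrollment, "Hospital providers will screen patients who have been admitted to the Labor and Delivery unit for eligibility", and the same providers ask eligible patients whether they are interested. Under Trial Coordination and Data Collection, two trained hospital providers do the examinations. No sentence requires these to be different people from those who screened or are treating the patient.

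**Whether an earlier dilation may be known.** Under Eligibility, one exclusion is "progression to the second stage of labor (i.e. known dilation of ten centimeters". Under Confidentiality, on identifiable patient information: "The hospital providers will likely have access to this information through the hospital medical record". Under Risks Related to the Study Device, study examination results are not used in clinical care, so any dilation used for care has to come from outside the study.

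**What is recorded.** The regression factors listed under Statistical Analysis are provider number, age, gestational age, weight, epidural status, and provider experience or training. Knowledge of an earlier dilation is not among them, nor among the items listed under Sources of Research Material.

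**The concern.** Two examiners can be kept apart perfectly and still not be independent if both start from the same earlier number. In the control arm the recorded value is the examiner's own estimate, which can drift towards a known value. In the device arm the value is read from a tape, photographed and later read by a reviewer, which leaves less room for drift.

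A shared earlier value would therefore tend to raise control agreement more than device agreement. Two things are at stake: the size of the estimated device effect, with the power to detect it, and the meaning of the control figure. A high control agreement could reflect good unaided examination or a shared starting point, and the data as planned could not tell these apart.

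**Working it through.** **Inputs.** All from Power Calculation and Statistical Analysis: "The agreement in the Control Group was projected to be 49" per cent; "the agreement in the Device Group was projected to be 90" per cent; SD 23; 25 per arm; "The statistical analysis will use a two-tailed level of significance of 0.05". The share k of affected pairs is not in the documents and is an assumption.

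**Step 1: the plan's own figure.** Treating agreement as a mean in percentage points, n per arm = 2 × (1.96 + 0.84)² × (23/41)² ≈ 4.9, so 5. At 5 per arm: 41 / (23 × √(2/5)) = 2.82; 2.82 − 1.96 = 0.86; power 80%. This matches "a sample size of five yields 80% power" if five means five per arm. At 25 per arm: 41 / (23 × √(2/25)) = 6.30; 6.30 − 1.96 = 4.34; power above 99.9%, matching the stated 100%.

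**Step 2: the same contrast as a yes/no outcome.** Each pair either agrees or does not. With d the difference, p̄ the mean of the two proportions, s0 = √(2p̄(1 − p̄)/25) and s1 = √([pC(1 − pC) + pD(1 − pD)]/25), power = Φ((d − 1.96 × s0)/s1). At 49% against 90% this is (0.41 − 1.96 × 0.1302)/0.1166 = 1.33, or 91%. Fisher's exact test gives 85%, and the t test on 0/1 outcomes gives 92%.

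**Step 3: illustration with a shared value.** Suppose a share k of pairs in both arms report the shared value and so agree. Then control = 0.49 + 0.51k, device = 0.90 + 0.10k, difference = 0.41 × (1 − k).

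| k | Control | Device | Difference (points) | Power, 25 per arm (step 2 formula) |
|---|---|---|---|---|
| 0 | 49.0% | 90.0% | 41.0 | 91% |
| 0.2 | 59.2% | 92.0% | 32.8 | 79% |
| 0.3 | 64.3% | 93.0% | 28.7 | 71% |
| 0.5 | 74.5% | 95.0% | 20.5 | 52% |

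For k = 0.2: (0.328 − 1.96 × 0.1215)/0.1123 = 0.80, hence 79%. On the plan's SD-23 scale the erosion is largely hidden: at k = 0.5, 20.5/6.505 − 1.96 = 1.19, or 88%.

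**Step 4: a milder model.** Here both examiners only lean towards the shared value. Assumptions: true dilation uniform from 2 to 8 cm, integer readings, independent errors set to give 49% and 90% agreement, and an earlier value with SD 1 cm around the truth. With weight 0.1, 0.2, 0.3 and 0.5 on the earlier value, simulated control agreement is about 53, 57, 62 and 72%, and device agreement 91, 92, 93 and 95%. The contrast is about 38, 35, 31 and 23 points.

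Both models give the same direction, because control has 51 points of room to rise and the device arm has 10.

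**The case against.** The case against has several sound parts.

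- **The evidence for prior knowledge is indirect.** A reader might infer that the screening staff are the examiners. The documents use similar terms for both and do not separate them, but they never say they are the same people. Each examiner introduces himself or herself to the patient, which fits, without requiring, someone new to her.
- **The Confidentiality paragraph is not an admission of chart review.** It concerns identifiable information in general and goes on to say that providers are not given the data through the trial. It shows likely access to the record, not that an examiner read a dilation.
- **The exclusion concerns only a known 10 cm.** Screening need not retrieve any other value, and some induction patients are not yet in labor.
- **The effect is conditional.** If only one examiner knows a value, or the two know different values, agreement need not rise.
- **The bias is conservative.** A reader might infer that a positive result would be unsafe. On this mechanism it would not: a shared value shrinks the contrast.
- **The baseline may not be clean.** The 49% comes from laboring women, and the documents do not show whether those examiners knew earlier values. If they did, step 3 counts part of the effect twice.
- **It may be a choice of estimand.** Control examiners use their regular technique, and regular practice may include the chart.

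All of this limits how strongly the point can be put. It does not close the gap. Even if the chart is meant to be part of usual practice, the plan does not say so, and without a record of prior knowledge the control figure cannot be read either way.

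**Conclusion.** The gap is real and the stated direction is probable, but only under a condition. The plan protects against one route by which readings can become dependent and leaves a second one open and unrecorded. If both examiners share the same earlier value, control agreement would probably rise more than device agreement. The illustration takes the 41-point contrast to about 33, 29 and 21 points at k = 0.2, 0.3 and 0.5.

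That range rests on an assumed k, on affected pairs agreeing outright, on equal effect in both arms, and on 49% and 90% being free of such influence. The documents establish none of these. They do not support a statement that the bias occurs, that it has any particular size, or that it could favor the device. The point is a low-cost improvement of lower priority.

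**What to change.** **Data Collection.** Before the allocation is revealed, the coordinator selects, where possible, two trained providers on shift who have not examined or screened this patient, or read her charted dilation, during this admission. Where no such pair is available, proceed and mark it. At present, randomization is described before the providers are called, so this step has to move ahead of it.

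**Data Collection Forms.** Add one item to each form, completed only after the study reading is recorded and that section folded: *Before this exam, did you know an earlier dilation for this patient? (yes/no; value)*. The order matters, because asking beforehand would itself prompt the earlier value.

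**Statistical Analysis.** Report the counts by arm, and pre-specify a descriptive sensitivity analysis of the primary outcome that excludes pairs in which both examiners knew an earlier value.

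**Cost.** One procedural sentence, one form item and one descriptive analysis, with no extra staff. Some sessions may be delayed: the training benchmark is only two providers and providers may opt out of busy shifts, so the proceed-and-mark route may be used often. With about 25 pairs per arm the subset analysis will be imprecise and should not be tested formally; the counts are informative in any case.

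### Randomizing straight after consent, before the two providers, re-affirmed consent and current eligibility are confirmed, lets some pre-exam losses fall after allocation; moving the step to the bedside would reduce them at little cost

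*Combined protocol and SAP*

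**What the plan says.** All references are to the combined protocol and SAP, mainly its Trial Protocol part.

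- **Order of steps.** After signed consent (Patient Enrollment), the Randomization paragraph has: "The trial coordinator will assign the participant a Subject Number from one to 50, in sequential order". Next: "The trial coordinator will then randomize the patient to either the Control Group or the Device Group". Data Collection then begins: "The trial coordinator will inform two trained providers that the patient has agreed to participate in the trial". The coordinator goes to the room with the first provider, and: "The trial coordinator will re-affirm consent with the patient". The exam follows. The Protocol Summary also places randomization after consent.
- **Eligibility.** The exclusions include "progression to the second stage of labor (i.e. known dilation of ten centimeters), non-English speaking, known prior rupture of membranes", and conditions needing an emergent or urgent cesarean. Women admitted for induction may consent before labor starts.
- **Scheduling and staffing.** Trial Coordination has the coordinator arrange "to conduct the trial at scheduled times during the study period", and states that running the trial takes two trained providers, the coordinator and a patient. Risks to Providers allows a provider to opt out of a shift when the unit is too busy.
- **Missing readings.** Under Statistical Analysis, "if a patient is missing one or both of the cervical dilation readings, she will be excluded from analysis of the primary outcome". Nothing is imputed. Subject Numbers end at 50, and no replacement rule or loss allowance is given.

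**The concern.** The same event counts differently on either side of randomization. Found before it, a ruptured membrane, a change of mind or an absent second provider is a screen failure with no effect on the comparison. Found after it, the event leaves a randomized woman without a pair of readings: she has used one of 50 numbers and drops out of the primary analysis. The coordinator knows her arm by then, and the trial is open label.

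Three routes run through the interval between allocation and the first exam. She may decline when consent is re-affirmed. She may have become ineligible. Or two providers may not be available. The first two depend on things that can change in labor, and the third on a step that the protocol places after the arm is assigned. At stake are a few avoidable post-randomization exclusions in a trial of 25 per arm and, less likely, an exam in a woman who no longer meets the criteria.

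**Working it through.** **1. The sequence.** The written order is: screening, consent, Subject Number, arm, providers told, room, consent re-affirmed, first exam. The only check at the bedside common to both arms is of consent. In the Device Group the first provider also asks whether the patient is ready, which is not an eligibility check.

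**2. What can change after allocation.** Three criteria can: membranes intact, not known to be 10 cm, no emergent or urgent cesarean condition. The time from allocation to exam is not stated. Because consent may precede labor, a gap is possible; because sessions are scheduled, it may be short.

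**3. What moving the step would and would not catch.**

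| Loss | Caught by randomizing at the bedside? |
|---|---|
| Declines when consent is re-affirmed | Yes |
| Known rupture, known 10 cm or urgent cesarean before the first exam | Yes, if present when checked |
| Two providers not available at the start | Yes |
| Withdraws after the first exam (Discomfort section) | No |
| Second exam not done within 10 minutes | No |

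**4. The plan's power figures.** Inputs from Power Calculation: 49% v 90% (41 points), SD 23, two-sided 0.05. Normal approximation: power = Φ(41 / (23·√(2/n)) − 1.96).
- n = 5 per group: 41 / 14.55 = 2.82; 2.82 − 1.96 = 0.86; power 80.5%. This matches the stated 80%, reading five as per group.
- n = 25 per group: 41 / 6.505 = 6.30; 6.30 − 1.96 = 4.34; power 99.999%. This matches the stated 100%.

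**5. Effect of losses on power.** The documents give no loss rate, so the counts below are assumptions. One loss is 1/25 = 4% of an arm. Column A uses the plan's inputs with the noncentral t distribution. Column B treats each pair as agree or disagree and applies the planned pooled t-test. With x and y agreeing pairs of n₁ and n₂, a = x/n₁ and b = y/n₂, the statistic is t = |a − b| / √(v(1/n₁ + 1/n₂)), where v = [x(1 − a) + y(1 − b)] / (n₁ + n₂ − 2). Power is the sum of Bin(x; n₁, 0.49)·Bin(y; n₂, 0.90) over all (x, y) with t above the 0.975 quantile on n₁ + n₂ − 2 df.

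| Pairs per arm | A: plan's inputs | B: agree/disagree |
|---|---|---|
| 25 / 25 | 99.999% | 92.3% |
| 24 / 24 | 99.998% | 91.0% |
| 23 / 23 | 99.996% | 89.5% |
| 20 / 20 (20% lost) | 99.98% | 85.4% |

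One or two losses per arm cost 0 points under A, and about 1 to 3 points under B (92.3 − 91.0 = 1.3; 92.3 − 89.5 = 2.8). Power is not the reason to act.

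**The case against.** Randomizing after signed consent is ordinary practice, and much of the risk is already contained. Sessions are scheduled and need two trained providers, and the opt-out is by shift, so a shortage would normally show before a patient is approached. Planned amniotomy is placed after both exams, which removes the most foreseeable cause of rupture. The exclusions concern what is known, the providers probably have the medical record (Confidentiality section), and an emergency would stop a research exam without a checklist. The post-allocation losses that the protocol describes most directly come after the first exam. Its remark that a survey is kept because "it may include important data accounting for why the patient was unable to have both examinations" fits those at least as well as losses before it.

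Most of this stands, and it limits the point. The provider route is less likely, the interval may be short, and the later losses are untouched by the change. What remains is that the protocol fixes an order in which the provider and consent checks come after the arm is assigned, and eligibility is not checked again at all. A short interval does not defend that order, since it also makes moving the step nearly free.

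**Conclusion.** The point holds as a modest, low-priority improvement. Randomizing last would reduce losses between allocation and the first exam; losses that occur before the allocation is opened could not depend on the arm. The gain cannot be sized from the documents and is probably small. This rests on reading the written order as the order that will be followed.

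Stronger readings that a reader might infer are not supported:

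- **That the present order biases the result.** The Bias section says that patients and providers cannot be blinded, but the documents do not show that providers know the arm before they reach the room. Nothing links rupture, an urgent cesarean or a busy shift before the exam to whether two readings would have agreed.
- **That moving the step prevents losses after allocation altogether.** Withdrawal after the first exam and a missed 10-minute limit remain.
- **That power is at risk.** It is not on the plan's inputs, and on an agree/disagree outcome the change is slight unless losses are far heavier than there is reason to assume.
- **That patients are endangered.** The protocol treats the infection risk of an extra exam as theoretical and at most minimal. Its placing of amniotomy after both exams shows that they are meant to precede rupture, but no hazard follows from the missing check alone.

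**What to change.** Keep consent where it is and move the assignment of the Subject Number and the opening of the allocation to the bedside, immediately before the first exam. Before opening it, the coordinator confirms that:

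1. two trained providers are available now;
2. consent is re-affirmed;
3. from the chart and the patient, membranes are intact, she is not known to be 10 cm, and there is no emergent or urgent cesarean condition.

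Women who do not pass are logged with the reason as not randomized and use none of the 50 numbers. The epidural criterion should not be re-applied to women who consented before labor. If randomization stays where it is, add the three eligibility items when consent is re-affirmed; that guards against exams in women no longer eligible but does not reduce losses after allocation.

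The cost is a reordered paragraph and a short check by a coordinator who is already in the room, with no extra patients and no change to the analysis. Two devices must be brought to every session, because each provider in the Device Group uses one. The photo background sheet has to be numbered at the bedside, and some women will be consented but not randomized.
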